8.2 Participant demographics/other baseline characteristics

Participant demographic and BSL characteristics data to be collected on all participants and to be recorded in the eCRF include:

- Year of birth, sex, race, predominant ethnicity (if permitted); Participant's race and
 ethnicity are collected and analyzed to identify variations in safety or efficacy due to these
 factors as well as to assess the diversity of the study population as required by Health
 Authorities.
- Relevant medical history/current medical conditions (until date of signature of informed consent) will also be recorded in the CRF. Where possible, diagnoses, not symptoms, should be recorded.

• All prescription medications, over-the-counter drugs and significant non-drug therapies prior to the start of the study must be documented in the Concomitant medications/ Significant non-drug therapies section of the CRF as outlined in Section 6.8.1.

Country-specific regulations should be considered for the collection of demographic and BSL characteristics in alignment with CRF.

Table 8-1 Eligibility assessments

Assessment	Description	Documentation
Shoulder X-Ray	To be performed in both shoulders (affected and contralateral) to exclude shoulder pathologies as per exclusion criteria (Section 5.2); historical shoulder X-rays are acceptable if obtained ≤3 months before BSL.	Source only
Shoulder MRI	Image analysis to be performed centrally to confirm evidence of tendinopathy and exclude other shoulder pathologies and tears (if present) >50% thickness and AP diameter >10mm; a centrally read MRI within 3 months from baseline may be accepted if already performed.	Database
Patient Reported Outcomes	To be performed to include participants experiencing moderate-severe symptoms based on WORC PRO and meeting specific pain criteria, as outlined in inclusion criteria (Section 5.1)	Database
Physical examination	See Section 8.4.1	Source only
Hematology, Clinical chemistry	via central laboratory	Database
RF/anti-CCP	via central laboratory; only performed at screening	Database
Tuberculosis test	QuantiFeron Gold	Database
Pregnancy and assessments of fertility	See Section 8.4.6	Database
Hepatitis B, C or HIV screening	Hepatitis B and/or hepatitis C and/or HIV serology testing to be performed locally during screening period only if required as per local medical practice or local regulations prior to initiation of therapy. These assessments will be done by central laboratory if no accredited local laboratory is available, and will be documented in the source only.	Source only
Painful Arc test	Painful arc test will be performed at screening and BSL in order to assess eligibility for inclusion criteria 4 (nocturnal pain in shoulder on 3 out of 7 nights prior to BSL also accepted to fulfill this criterion if Painful Arc test is negative).	Database

8.2.1 Shoulder X-ray

An X-ray of the shoulder will be taken during Screening in order to rule-out other shoulder conditions, as outlined in Section 5.2. If a historic X-ray is available from within 3 months of BSL, then this will be accepted. It is recommended that the x-ray is performed in anterior-posterior and lateral planes in order to evaluate the shoulder.

8.2.2 Shoulder MRI

MRI images will be acquired at 1.5 T or greater in multiple planes by using an imaging sequence optimized for tendon/surrounding tissue separation and adapted to the MRI system capabilities. The MRI read should be performed centrally during the screening period. However, centrally read shoulder MRIs performed within 3 months of BSL may also be accepted (provided that

the quality of the images is deemed sufficient). Detailed information on the MRI procedure can be found in the imaging manual. The coded MRI medical images will be used primarily for analysis as described in this protocol; however, the images may also be used for the development and evaluation of new analysis methods directly related to the area of research that this study covers.

8.2.3 Tuberculosis screening

The QuantiFERON TB-Gold test will be analyzed by the central laboratory. Details on the collection, processing and shipment of samples and reporting of results by the central laboratory are provided in the laboratory manual. The results must be known prior to randomization to determine the participant's eligibility for the study.

Participants with a positive test may participate in the study if further work up (according to local practice/guidelines) establishes conclusively that

- the participant has no evidence of active tuberculosis
- if presence of latent tuberculosis is established then treatment according to local country guidelines must have been initiated prior to enrollment.

Participants with indeterminate test result should repeat test once more as soon as possible. If subsequent test result is positive, further work up is required, as outlined above.

Any significant findings should be recorded in the eCRF.

8.2.4 Painful Arc test

[figure not shown]
The Painful Arc test will be performed at screening and BSL in order to assess eligibility as outlined in Section 5.1. The result will be reported as a negative or positive result, with a positive result indicated by participant expressing pain between 60-120°. The test should be performed in both shoulders, actively and passively.

8.3 Efficacy assessments

Planned time points for all efficacy assessments are provided in Section 1.3 Schedule of Activities. The following key assessments are PROs and therefore described in Section 8.5.1:

- WORC Index
- •
- PROMIS-SF Upper Extremity
- •
- •
- •

These will be collected on an electronic device that will be used at the participants' home and on site.

8.3.4 Appropriateness of efficacy assessments

The efficacy assessments selected are commonly used in studying this and similar indications.

8.4 Safety assessments

Safety assessments are specified below with Section 1.3 Schedule of Activities detailing when each assessment is to be performed.

For details on AE collection and reporting, refer to the Section 8.6.

Evaluation of all AEs and SAEs including injection site reactions, physical examination, vital signs and laboratory assessments will occur. Anti-secukinumab antibody development (immunogenicity) will also be evaluated.

All blood draws and safety assessments should be done prior to study treatment administration. Appropriate safety assessments (e.g., evaluation of AEs and SAEs including injection site reactions) should be repeated after the dose is administered.

- Physical examination
- Height and weight
- Vital signs
- Laboratory evaluations (Hematology, Clinical Chemistry)
- Evaluation of AE/SAEs
- Pregnancy
- Tolerability of secukinumab
- Immunogenicity

As per Section 4.5, during a public health emergency as declared by local or regional authorities i.e. pandemic, epidemic or natural disaster, that limits or prevents on-site study visits, regular phone or virtual calls can occur (according to visit schedule or more frequently if needed) for

Page **61** of **107**

Protocol No. CAIN457O12301

safety monitoring and discussion of the participant's health status until it is safe for the participant to visit the site again.

8.4.1 Physical examinations

The physical examination will include the examination of general appearance, skin, neck, eyes, ears, nose, throat, lungs, heart, abdomen, back, lymph nodes, extremities, vascular and neurological system.

Information for all physical examinations must be included in the source documentation at the study site. Significant findings that are present before signing the ICF must be included in the relevant medical history eCRF. Significant findings made after signing the ICF that meet the definition of an AE must be recorded in the AE eCRF and if SAE criteria are met, also reported as a SAE.

Investigators should pay special attention to clinical signs related to previous serious illnesses.

ROM assessments will be performed throughout the study to physically assess shoulder (see Section 8.3.1). Painful arc test will also be performed in order to assess eligibility (see Section 8.2.4)

8.4.2 Height and weight

Height in centimeters (cm) and body weight (to the nearest 0.1 kilogram [kg] in indoor clothing) (both without shoes) will be measured. If possible, body weight assessments should be performed by the same study site staff member using the same scale throughout the study.

Body mass index (BMI) will be calculated using the following formula:

• BMI = Body weight (kg) / [Height (m)]²

8.4.3 Vital signs

Vital signs include blood pressure (BP) and pulse measurements. After the participant has been sitting for five minutes, with the back supported and both feet placed on the floor, systolic and diastolic blood pressure will be measured using an automated validated device, e.g., OMRON, with an appropriately sized cuff. In case the cuff sizes available are not large enough for the participant's arm circumference, a sphygmomanometer with an appropriately sized cuff may be used.

If possible, vital sign assessments should be performed by the same study site staff member using the same validated device throughout the study.

No specific action is pre-defined within this protocol to respond to specific abnormal vital signs, as it will be decided by the Investigator whether and which specific action needs to be taken to respond to any abnormal values, taking into account the overall status of the participant.

8.4.4 Electrocardiograms

Not applicable

8.4.5 Clinical safety laboratory tests

A central laboratory will be used for analysis of all blood specimens detailed in this section, unless otherwise specified. Samples will be collected according to the assessment schedule.

Details on the collections, shipment of samples, and reporting of results by the central laboratory will be provided to Investigators in the central laboratory manual.

Clinical site practice will be applied for point-of-care tests (urine pregnancy testing). Adequate documentation of these test results needs to be maintained in the participant's source documentation.

Clinically notable laboratory findings are defined in Section 10.3.

Clinically significant abnormalities must be recorded as either medical history/current medical conditions or adverse events as appropriate. All participants with laboratory tests containing clinically significant abnormal values should be followed until the values return to normal ranges or until a valid reason, other than treatment related AE, is defined.

As per Section 4.5, during a public health emergency as declared by local or regional authorities, i.e., pandemic, epidemic or natural disaster, that limits or prevents on-site study visits, if participants cannot visit the site for protocol-specified safety lab assessments, an alternative lab (local) collection site may be used.

Table 8-2 Laboratory assessments

Test Category	Test Name
Hematology	Erythrocyte Cell Morphology, Hemoglobin, Leukocytes, Platelets, Differential (Basophils, Eosinophils, Lymphocytes, Monocytes, Neutrophils, Other (absolute value and %))
Chemistry	Albumin, Alkaline phosphatase (ALP), ALT, Amylase, AST, Calcium, Creatinine, Direct Bilirubin, Glucose (non-fasting), Lactate dehydrogenase (LDH), Lipase, Magnesium, Phosphate, Potassium, Sodium, Total Bilirubin, Urea Nitrogen or Urea, Uric Acid,
Pregnancy Test	Serum / Urine pregnancy test (refer to 'Pregnancy testing', Section 8.4.6) Urine dipstick to be assessed locally.

8.4.6 Pregnancy testing

All pre-menopausal women who are not surgically sterile will have pregnancy testing. Kits will be provided by the central laboratory. A serum β -hCG test will be performed in all women of childbearing potential at Screening. All pre-menopausal women who are not surgically sterile at Screening will have local urine pregnancy tests as indicated in Table 1-1. A positive urine pregnancy test requires immediate interruption of study treatment until an unscheduled serum β -hCG is performed and found to be negative. If positive, the participant must be discontinued from the trial. Additional pregnancy testing might be performed if requested per local requirements. Refer to Section 8.6.4 for details of reporting of pregnancy.

Effective methods of birth control must be used for women of childbearing potential (see exclusion criteria definitions, Section 5.2).

As per Section 4.5, during a public health emergency as declared by local or regional authorities, i.e., pandemic, epidemic or natural disaster, that limits or prevents on-site study visits, if participants cannot visit the site to have serum pregnancy tests, urine pregnancy test kits may be used. Relevant participants can perform the urine pregnancy test at home and report

the result to the site. It is important that participants are instructed to perform the urine pregnancy test first and only if the test result is negative proceed with the administration of the study treatment. A communication process should be established with the participant so that the site is informed and can verify the pregnancy test results (e.g., following country specific measures).

Assessments of fertility

A woman is considered of childbearing potential from menarche and until becoming postmenopausal unless permanently sterile. Permanent sterilization methods include hysterectomy, bilateral salpingectomy and bilateral oophorectomy. Medical documentation of oophorectomy, hysterectomy, or tubal ligation must be retained as source documents.

A postmenopausal state is defined as no menses for 12 months without an alternative medical cause and an appropriate clinical profile.

In absence of the medical documentation confirming permanent sterilization, or if the postmenopausal status is not clear, the Investigator should use his medical judgment to appropriately evaluate the fertility state of the woman and document it in the source document.

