1.3 Schedule of activities (SoA)

The SoA lists all of the assessments when they are performed. All data obtained from these assessments must be supported in the participant's source documentation. The "X" in the table denotes the assessments to be recorded in the clinical database or received electronically from a vendor. The "S" in the table denotes the assessments that are only in the participant's source documentation and do not need to be recorded in the clinical database.

If the Investigator deems it feasible and subject to adequate training, the participants may be able to administer study drug at home (self-administered or administered by caregiver) at Week 1 and Week 3. Participant or caregiver must demonstrate their ability to administer study drug at the BSL visit at the site before home administration is permitted. Tele-visits, i.e., secure videoconferencing, between the Participant and Investigator may also be utilized as additional support for administration of study drug at home.

Participants should be seen for all visits/assessments as outlined in the SoA or as close to the designated day/time as possible. Missed or rescheduled visits should not lead to automatic discontinuation.

Participants who discontinue from study treatment should still attend all visits until End of Study (EOS) as indicated in the SoA.

Participants who discontinue from study should be scheduled for a final evaluation visit (EOT assessments should be performed as final evaluation, or EOS if participant has already completed EOT at Week 16) if they agree, as soon as possible, at which time all of the assessments listed for the EOT visit will be performed. At this final visit, the AEs and concomitant medications not previously reported must be recorded on the Case Report Form (CRF).

Pharmacokinetic samples should be taken prior to study drug administration.

Patient Reported Outcomes (PRO) questionnaires must be completed before any assessments are performed at any given visit.

Repeat or unscheduled samples may be taken for safety reasons or for technical issues with the samples, or unscheduled safety assessments may be performed at the discretion of the Investigator if there is a concern or need follow up for an AE.

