7.1 Discontinuation of study treatment

Discontinuation of study treatment for a participant occurs when study treatment is permanently stopped for any reason (prior to the End of Treatment, if any) and can be initiated by either the participant or the Investigator.

The Investigator must discontinue study treatment for a given participant if, he/she believes that continuation would negatively impact the participant's well-being.

Discontinuation from study treatment is required under the following circumstances:

- Participant/guardian decision
- Pregnancy
- Use of specified prohibited treatment as per recommendations in the prohibited treatment section
- Any situation in which continued study participation might result in a safety risk to the participant
- Following emergency unblinding

- AEs, abnormal laboratory values or abnormal test result that indicate a safety risk to the participant.
- Unsatisfactory therapeutic effect
- Participant's condition no longer requires study treatment
- Emergence of the following AEs:
 - 1. Any AE that in the judgement of the Investigator, taking into account the participant's overall status, prevents the participant from continuing study treatment.
 - 2. Any severe or serious AE that requires treatment with a prohibited medication
 - 3. Severe hypersensitivity reaction or anaphylactic shock (see Section 8.6.1)
- Any laboratory abnormalities that in the judgment of the Investigator, taking into consideration the participant's overall status prevents the participant from continuing participation in the study

If discontinuation from study treatment occurs, the Investigator should make a reasonable effort to understand the primary reason for the participant's discontinuation from study treatment and record this information.

Participants who discontinue from study treatment agree to return for the end of treatment and follow-up visits indicated in Section 1.3 Schedule of Activities.

Participants who **agree to continue attending study** visits following treatment discontinuation should continue attending all subsequent scheduled site visits for clinical and safety study assessments until Week 24 End of Study visit. Participants initially continuing to attend site visits after premature study treatment discontinuation may subsequently decide to discontinue the study at any time.

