7.2 Participant discontinuation from the study

Discontinuation from study is when the participant permanently stops receiving the study treatment, and further protocol-required assessments or follow-up, for any reason.

If the participant agrees, a final evaluation at the time of the participant's study discontinuation should be made as detailed in Section 1.3 Schedule of Activities.

Participants who are prematurely withdrawn from the study will not be replaced.

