8.5.1 Clinical Outcome Assessments (COAs)

8.5.1.1 Patient reported outcomes (PRO)

PROs will be completed at the scheduled visits as outlined in Table 1-1 using an electronic device. Please note that all scoring calculations will be performed electronically by the device and scores required for inclusion to study will be available for review by the Investigator.

Site and participants will receive appropriate training and guidance on the use of the electronic device and will receive clear instructions on the completion of the assessments.

All questionnaires will be available in the local languages of the participating countries.

Participants should complete the PRO measures before any clinical assessments are performed at a given visit. Participants will be given sufficient instruction, space, time and privacy to complete all study PROs. The study coordinator will check the responses to the questionnaire for completeness and encourage the participant to complete any missing responses. If participants have trouble with submission after they complete the PROs, the study staff will assist them with submitting their PRO responses. Attempts should be made to collect responses to all PROs for all participants, including participants who prematurely discontinue the study prior to the end of treatment visit. Participant's refusal to complete all or any part of a PRO measure should be documented in the study data capture system/study source records and should not be captured as a protocol deviation. Handling of protocol deviations can be modified if needed per study protocol.

Exceptionally, if there is an issue with the electronic device, there will be a web-based alternative.

The participant should be made aware that completed measure(s) are not reviewed by the Investigator/study personnel and that they should report any discomfort, unusual symptoms or medical problems directly to the Investigator/study personnel, according to the ICF. A reminder should be implemented in ePRO with the support of External Development Operations.

The following instruments will assess the impact of RCT on various aspects of participant's physical function, pain, and health-related quality of life (QoL):

The Western Ontario Rotator Cuff Index (WORC)

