8.6.4 Pregnancy

- Details of all pregnancies in female participants will be collected after the start of study treatment and until the end of study participation (or longer depending on local contraceptive requirements, as outlined in Section 5.2).
- While pregnancy itself is not considered to be an AE or SAE, any pregnancy complication or elective termination of a pregnancy for medical reasons will be reported as an AE or SAE.
- Abnormal pregnancy outcomes (e.g., spontaneous abortion, fetal death, stillbirth, congenital anomalies, ectopic pregnancy) are considered SAEs and will be reported as such.
- Any post study pregnancy-related SAE considered reasonably related to the study treatment by the Investigator will be reported to Novartis as described in Section 8.6.3. While the Investigator is not obligated to actively seek this information in former study participants, he or she may learn of an SAE through spontaneous reporting.

If a female trial participant becomes pregnant, the study treatment should be stopped, and the pregnancy consent form should be presented to the trial participant. The participant must be given adequate time to read, review and sign the pregnancy consent form. This consent form is

necessary to allow the Investigator to collect and report information regarding the pregnancy. To ensure participant safety, each pregnancy occurring after signing the informed consent must be reported to Novartis within 24 hours of learning of its occurrence. The pregnancy should be followed up to determine outcome, including spontaneous or voluntary termination, details of the birth, and the presence or absence of any birth defects, congenital abnormalities, or maternal and/or newborn complications.

Pregnancy should be recorded and reported by the Investigator to the Novartis Chief Medical Office and Patient Safety (CMO&PS). Pregnancy follow-up should be recorded on the same form and should include an assessment of the possible relationship to the study treatment any pregnancy outcome. Any SAE experienced during pregnancy must be reported.

After consent is provided, the pregnancy reporting will occur up to one year after the estimated date of delivery.

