Start of the clinical trial	The start of the clinical trial is defined as the signature of the informed consent by the first participant
Study treatment	Any drug or combination of drugs or intervention administered to the study participants as part of the required study procedures; includes investigational drug(s), control(s) or background therapy
Study treatment discontinuation	When the participant permanently stops taking any of the study drug(s) prior to the defined study treatment completion date (if any) for any reason; may or may not also be the point/time of study discontinuation
Tele-visit	Procedures or communications conducted using technology such as telephone or video- conference, whereby the participant is not at the investigative site where the Investigator will conduct the trial.
Treatment arm/group	A treatment arm/group defines the dose and regimen or the combination, and may consist of 1 or more cohorts.
Treatment of interest	The treatment of interest and, as appropriate, the alternative treatment to which comparison will be made. These might be individual interventions, combinations of interventions administered concurrently, e.g. as add-on to standard of care, or might consist of an overall regimen involving a complex sequence of interventions. This is the treatment of interest used in describing the related clinical question of interest, which might or might not be the same as the study treatment.
Variable (or endpoint)	The variable (or endpoint) to be obtained for each participant that is required to address the clinical question. The specification of the variable might include whether the participant experiences an intercurrent event.
Withdrawal of consent	Withdrawal of consent from the study occurs when the participant explicitly requests to stop use of their data and/or biological samples AND no longer wishes to receive study treatment, AND does not agree to further protocol required assessments. This request should be in writing (depending on local regulations) and recorded in the source documentation. This request should be distinguished from a request to discontinue the study. Other study participant's privacy rights are described in the corresponding informed consent form.

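### The pregnancy-testing section orders exit from the trial, while the follow-up rules keep participants who stop treatment on visits to Week 24 and the primary estimand uses their data

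*Protocol*

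**What the plan says.** Protocol Section 8.4.6 has a positive urine test interrupt dosing until a serum test is done. It then states: "If positive, the participant must be discontinued from the trial".

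The protocol separates leaving the study from stopping treatment. Section 7.2: "Discontinuation from study is when the participant permanently stops receiving the study treatment, and further protocol-required assessments or follow-up, for any reason". The glossary in Section 10.2.2 says that stopping study treatment "may or may not also be the point/time of study discontinuation".

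Elsewhere, pregnancy is a reason to stop treatment:
- Section 7.1 lists it under the heading "Discontinuation from study treatment is required under the following circumstances", and says that participants who stop treatment "agree to return for the end of treatment and follow-up visits indicated in Section 1.3".
- Section 8.6.4: "If a female trial participant becomes pregnant, the study treatment should be stopped".
- Section 1.3: "Participants who discontinue from study treatment should still attend all visits until End of Study (EOS) as indicated in the SoA".

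The primary estimand (Section 3.1) applies a treatment-policy strategy to treatment discontinuation for any reason, and Section 9.3.2 uses the data collected afterwards.

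**The concern.** For a pregnant participant who is willing to stay, Section 8.4.6 ends the scheduled visits that Sections 1.3 and 7.1 would continue. Stopping treatment is common to all the sections, and an exit does satisfy that part. The disagreement is about follow-up.

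Two things are at stake. First, a woman exposed to the drug early in pregnancy would lose scheduled visits, although nothing in the protocol explains why. Second, the treatment-policy estimand needs outcomes after treatment stops, and a compulsory exit creates missing data where the participant would have supplied them. After a positive test at Week 16 or 20 no dose is left to withhold, because the last one is given at Week 12, so the clause can only end follow-up.

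**Working it through.** **Inputs.** Visit days come from Protocol Table 1-2: Week 4 = 29, Week 8 = 57, Week 12 = 85, Week 16 = 113, Week 20 = 141, Week 24 = 169. Post-baseline urine tests fall at these six visits. Doses are given on Day 1 and at Weeks 1, 2, 3, 4, 8 and 12. AE and SAE collection runs to 12 weeks (84 days) after the last dose (Sections 8.6.1 and 8.6.3). The SAP's Week 16 window for WORC PSD is Days 100 to 127 (Table 2-1).

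**Assumptions.** Time is counted from the visit with the positive urine test, and that visit's dose is withheld.

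**Formulas.** Scheduled follow-up lost = 169 − test day. End of AE/SAE collection = last dose day + 84.

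| Positive test at | Later visits lost | Days lost to Week 24 | Last dose day | AE/SAE collection to |
|---|---|---|---|---|
| Week 4 | 5 | 169 − 29 = 140 | 22 | 22 + 84 = Day 106 |
| Week 8 | 4 | 169 − 57 = 112 | 29 | 29 + 84 = Day 113 |
| Week 12 | 3 | 169 − 85 = 84 | 57 | 57 + 84 = Day 141 |
| Week 16 | 2 | 169 − 113 = 56 | 85 | 85 + 84 = Day 169 |
| Week 20 | 1 | 169 − 141 = 28 | 85 | Day 169 |
| Week 24 | 0 | 0 | 85 | Day 169 |

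**Primary endpoint.** On study discontinuation, Section 1.3 offers one final evaluation, as soon as possible, if the participant agrees. Positive tests on Days 29, 57 and 85 come 71, 43 and 15 days before Day 100, so a prompt final evaluation would miss the Week 16 window. Three of the six post-baseline tests therefore put the Week 16 value at risk.

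The value is not necessarily lost. The PSD is completed at home in the e-diary, and Section 8.5.1.1 says: "Attempts should be made to collect responses to all PROs for all participants, including participants who prematurely discontinue the study".

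**Power.** Section 9.9.1 states about 95% for 117 per arm, difference 14, SD 30, two-sided 5%, two-sample z-test. Power = Φ(14 / (30√(2/n)) − 1.96).
- n = 117: Φ(3.569 − 1.96) = Φ(1.609) = 94.6%, which reproduces the stated figure.
- n = 116, one loss per arm: Φ(3.554 − 1.96) = Φ(1.594) = 94.5%.
- Five losses in total, split evenly (n = 114.5): 94.2%.

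The documents give no expected number of pregnancies, so one to five losses is an illustrative range.

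**The case against.** **Loose wording.** Section 8.4.6 says trial, while Section 7.2 defines discontinuation from study. The sentence before it concerns interrupting treatment, and Section 8.6.4, which it cites for pregnancy reporting, asks only that treatment stop. A site might reach the treatment-only meaning. But the protocol distinguishes the two kinds of discontinuation, and a mandatory instruction should not depend on a site reading it down.

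**Deliberate exception.** A specific rule may override a general one. Section 2.3 says that women unlikely to comply reliably with contraception should not continue in the study, and inclusion criterion 2 admits only non-pregnant women. Those passages concern contraceptive compliance and entry, however. Section 7.1 places pregnancy inside the general rule, and neither it nor Section 1.3 states an exception. If exit is intended, the sections still need reconciling.

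**Safeguards.** This argument has most force. Besides the AE/SAE collection shown above, a final evaluation is offered if she agrees. Section 4.7 provides a safety call 60 days after the last dose if she does not attend. With consent, pregnancy reporting runs to one year after the estimated delivery date, well beyond Week 24. These limit the safety consequence but do not replace the scheduled visits, and pregnancy reporting does not supply a Week 16 PSD score.

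**The Section 7.1 visits.** For participants who decline further attendance, Section 7.1 provides visits 4 and 12 weeks after the last dose. If applied here, the 12-week visit would fall on Day 106 or 113 after a positive test at Week 4 or 8, inside the Week 16 window. After a positive test at Week 12 the two visits fall on Days 57 + 28 = 85 and 57 + 84 = 141, both outside it. The provision is written for people who decline, so its use for a mandated exit is arguable. Without it, a willing pregnant participant could be scheduled for fewer visits than one who refuses.

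**The estimand.** Treatment policy does not forbid study discontinuation, and the protocol's MMRM handles missing values under a missing-at-random assumption. That is correct, but it does not justify creating missing data that could have been avoided.

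**Conclusion.** The concern holds, as a minor one. Section 8.4.6 conflicts with the follow-up rules in Sections 1.3 and 7.1 and works against the data collection that the primary estimand relies on. For each affected participant it ends between 0 and 5 scheduled visits (0 to 140 days). Positive tests at Weeks 4, 8 and 12 put the Week 16 PSD at risk without making its loss certain.

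This rests on reading discontinuation from the trial as Section 7.2 defines discontinuation from the study, and on a prompt final evaluation. No bias in a result is claimed. Few participants would be affected, and the effect on planned power is negligible. The SAP reports 21 participants randomized at termination, is now purely descriptive and omits superiority testing, so no current analysis changes. The clause still had practical force, because the SAP let participants screened by May 7, 2024 continue under the protocol to completion.

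**What to change.** Reword the sentence in Section 8.4.6 so that, after a positive serum test, the participant must be discontinued from study treatment (if ongoing) and, if she agrees, continues scheduled visits to the end of study. Add cross-references to Sections 1.3 and 7.1; Section 8.6.4 is already cited. If exit really is intended, give the reason and state the exception in Sections 1.3 and 7.1 instead.

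The cost is one sentence and two cross-references in an amendment, with no new procedure, and she keeps her choice about attending. Section 9.4.1 describes a second study of identical design, CAIN457O12302. Its protocol is not among the documents reviewed, so the sponsor should check it for the same clause.
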